#### 8.3.3.2 RELATIONSHIP TO STUDY INTERVENTION

All adverse events (AEs) must have their relationship to study intervention assessed by the clinician who examines and evaluates the participant based on temporal relationship and his/her clinical judgment. The degree of certainty about causality will be graded using the categories below. In a clinical trial, the study product must always be suspect.

- **Related** – The AE is known to occur with the study intervention, there is a reasonable possibility that the study intervention caused the AE, or there is a temporal relationship between the study intervention and event. Reasonable possibility means that there is evidence to suggest a causal relationship between the study intervention and the AE.
- **Not Related** – There is not a reasonable possibility that the administration of the study intervention caused the event, there is no temporal relationship between the study intervention and event onset, or an alternate etiology has been established.

OR

- **Definitely Related** – There is clear evidence to suggest a causal relationship, and other possible contributing factors can be ruled out. The clinical event, including an abnormal laboratory test result, occurs in a plausible time relationship to study intervention administration and cannot be explained by concurrent disease or other drugs or chemicals. The response to withdrawal of the

study intervention (dechallenge) should be clinically plausible. The event must be pharmacologically or phenomenologically definitive, with use of a satisfactory rechallenge procedure if necessary.

- **Probably Related** – There is evidence to suggest a causal relationship, and the influence of other factors is unlikely. The clinical event, including an abnormal laboratory test result, occurs within a reasonable time after administration of the study intervention, is unlikely to be attributed to concurrent disease or other drugs or chemicals, and follows a clinically reasonable response on withdrawal (dechallenge). Rechallenge information is not required to fulfill this definition.
- **Potentially Related** – There is some evidence to suggest a causal relationship (e.g., the event occurred within a reasonable time after administration of the trial medication). However, other factors may have contributed to the event (e.g., the participant's clinical condition, other concomitant events). Although an AE may rate only as "possibly related" soon after discovery, it can be flagged as requiring more information and later be upgraded to "probably related" or "definitely related", as appropriate.
- **Unlikely to be related** – A clinical event, including an abnormal laboratory test result, whose temporal relationship to study intervention administration makes a causal relationship improbable (e.g., the event did not occur within a reasonable time after administration of the study intervention) and in which other drugs or chemicals or underlying disease provides plausible explanations (e.g., the participant's clinical condition, other concomitant treatments).
- **Not Related** – The AE is completely independent of study intervention administration, and/or evidence exists that the event is definitely related to another etiology. There must be an alternative, definitive etiology documented by the clinician.

### 8.3.3.3 EXPECTEDNESS

[name] will be responsible for determining whether an adverse event (AE) is expected or unexpected. An AE will be considered unexpected if the nature, severity, or frequency of the event is not consistent with the risk information previously described for the study intervention.

### 8.3.4 TIME PERIOD AND FREQUENCY FOR EVENT ASSESSMENT AND FOLLOW-UP

The occurrence of an adverse event (AE) or serious adverse event (SAE) may come to the attention of study personnel during study visits and interviews of a study participant presenting for medical care, or upon review by a study monitor.

All AEs including local and systemic reactions not meeting the criteria for SAEs will be captured on the appropriate case report form (CRF). Information to be collected includes event description, time of onset, clinician's assessment of severity, relationship to study product (assessed only by those with the training and authority to make a diagnosis), and time of resolution/stabilization of the event. All AEs occurring while on study must be documented appropriately regardless of relationship. All AEs will be followed to adequate resolution.

Any medical condition that is present at the time that the participant is screened will be considered as baseline and not reported as an AE. However, if the study participant's condition deteriorates at any time during the study, it will be recorded as an AE.

Changes in the severity of an AE will be documented to allow an assessment of the duration of the event at each level of severity to be performed. AEs characterized as intermittent require documentation of onset and duration of each episode.

[name] will record all reportable events with start dates occurring any time after informed consent is obtained until 7 (for non-serious AEs) or 30 days (for SAEs) after the last day of study participation. At each study visit, the investigator will inquire about the occurrence of AE/SAEs since the last visit. Events will be followed for outcome information until resolution or stabilization.

---

#### 8.3.5 ADVERSE EVENT REPORTING

[name] will record all reportable events with start dates occurring any time after informed consent is obtained until 7 (for non-serious AEs) or 30 days (for SAEs) after the last day of study participation.

---

#### 8.3.6 SERIOUS ADVERSE EVENT REPORTING

The study investigator shall complete an Unanticipated Adverse Device Effect Form and submit to the study sponsor and to the reviewing Institutional Review Board (IRB) as soon as possible, but in no event later than 10 working days after the investigator first learns of the effect. The study sponsor is responsible for conducting an evaluation of an unanticipated adverse device effect and shall report the results of such evaluation to the Food and Drug Administration (FDA) and to all reviewing IRBs and participating investigators within 10 working days after the sponsor first receives notice of the effect. Thereafter, the sponsor shall submit such additional reports concerning the effect as FDA requests.

---

#### 8.3.7 REPORTING EVENTS TO PARTICIPANTS

Not applicable.

---

#### 8.3.8 EVENTS OF SPECIAL INTEREST

Not applicable.

---

#### 8.3.9 REPORTING OF PREGNANCY

Not applicable.

---

### 8.4 UNANTICIPATED PROBLEMS

---

#### 8.4.1 DEFINITION OF UNANTICIPATED PROBLEMS (UP)

The Office for Human Research Protections (OHRP) considers unanticipated problems involving risks to participants or others to include, in general, any incident, experience, or outcome that meets all of the following criteria:

- Unexpected in terms of nature, severity, or frequency given (a) the research procedures that are described in the protocol-related documents, such as the Institutional Review Board (IRB)-approved research protocol and informed consent document; and (b) the characteristics of the participant population being studied;
- Related or possibly related to participation in the research (“possibly related” means there is a reasonable possibility that the incident, experience, or outcome may have been caused by the procedures involved in the research); and
- Suggests that the research places participants or others at a greater risk of harm (including physical, psychological, economic, or social harm) than was previously known or recognized.

This definition could include an unanticipated adverse device effect, any serious adverse effect on health or safety or any life-threatening problem or death caused by, or associated with, a device, if that effect, problem, or death was not previously identified in nature, severity, or degree of incidence in the investigational plan or application (including a supplementary plan or application), or any other unanticipated serious problem associated with a device that relates to the rights, safety, or welfare of subjects (21 CFR 812.3(s)).

#### 8.4.2 UNANTICIPATED PROBLEM REPORTING

The investigator will report unanticipated problems (UPs) to the reviewing Institutional Review Board (IRB) and to the Data Coordinating Center (DCC)/lead principal investigator (PI). The UP report will include the following information:

- Protocol identifying information: protocol title and number, PI's name, and the IRB project number;
- A detailed description of the event, incident, experience, or outcome;
- An explanation of the basis for determining that the event, incident, experience, or outcome represents an UP;
- A description of any changes to the protocol or other corrective actions that have been taken or are proposed in response to the UP.

To satisfy the requirement for prompt reporting, UPs will be reported using the following timeline:

- UPs that are serious adverse events (SAEs) will be reported to the IRB and to the DCC/study sponsor within 30 days of the investigator becoming aware of the event.
- Any other UP will be reported to the IRB and to the DCC/study sponsor within 30 days of the investigator becoming aware of the problem.
- All UPs should be reported to appropriate institutional officials (as required by an institution's written reporting procedures), the supporting agency head (or designee), and the Office for Human Research Protections (OHRP) within 30 days of the IRB's receipt of the report of the problem from the investigator.

An investigator shall submit to the sponsor and to the reviewing Institutional Review Board (IRB) a report of any unanticipated adverse device effect occurring during an investigation as soon as possible, but in no event later than 10 working days after the investigator first learns of the effect (21 CFR 812.150(a)(1)). A sponsor who conducts an evaluation of an unanticipated adverse device effect under

812.46(b) shall report the results of such evaluation to the Food and Drug Administration (FDA) and to all reviewing IRB's and participating investigators within 10 working days after the sponsor first receives notice of the effect. Thereafter the sponsor shall submit such additional reports concerning the effect as FDA requests (21 CFR 812.150(b)(1)).

#### 8.4.3 REPORTING UNANTICIPATED PROBLEMS TO PARTICIPANTS

Not applicable.

### 9 STATISTICAL CONSIDERATIONS

#### 9.1 STATISTICAL HYPOTHESES

- Primary Efficacy Endpoint(s):

The Smith and Nephew PICO NPWT dressing is superior to the standard cesarean incision dressing in preventing surgical site occurrences.

Null: The Smith and Nephew PICO NPWT dressing is NOT superior to the standard cesarean incision dressing in preventing surgical site occurrences.

- Secondary Efficacy Endpoint(s):

The Smith and Nephew PICO NPWT dressing is superior to the standard cesarean incision dressing in preventing surgical site infections.

Null: The Smith and Nephew PICO NPWT dressing is NOT superior to the standard cesarean incision dressing in preventing surgical site infections.

#### 9.2 SAMPLE SIZE DETERMINATION

- Outcome measure used for calculations (almost always the primary variable): incidence of surgical site occurrences.
- Type I error rate (alpha): 0.05 (5%)
- Power level: 80%

Based on results from several clinical studies and the American Congress of OBGYN Practice Bulletin on Obesity in Pregnancy, we estimate the proportion of subjects with surgical site occurrences among obese women who undergo elective cesarean surgery to be about 18%. We accept that an absolute difference between study groups of 10%, will be a clinically meaningful difference. Therefore, a chi-square test will yield 80% power to detect a clinically important difference of 10% between study groups (SOC proportion of 18% vs. PICO NPWT proportion of 8%, an odds ratio of 0.396) when the sample size

in each group is 180 *evaluable* subjects. Assuming an attrition rate of about 10%, we would need to recruit about 200 subjects per group (180/0.90=200 subjects).

Note: A study participant is considered 'evaluable' if she has completed all phases of the study including the last visit of the last scheduled procedure in the schedule of activities, i.e. the final study visit 4—day 42±10 days post-op.

### 9.3 POPULATIONS FOR ANALYSES

The primary statistical analysis will be based on a modified intention-to-treat (participants who underwent surgery and received the intervention). All subjects will be analyzed according to the intention-to-treat [ITT] principle. A patient will be considered evaluable and will be included in the intention-to-treat analysis if the patient has completed all phases of the study including the last visit of the last scheduled procedure in the schedule of activities, i.e. the final study visit 4—day 42±10 days post-op. Analyses that take into account the actual treatment received (e.g. use of PICO NPWT dressing for a minimum 5 days) will be carried out as a secondary analysis (per protocol [PP] analysis).

This was chosen to avoid various misleading artifacts that can arise in intervention research such as non-random attrition of participants from the study or crossover. Subjects strayed from the protocol (for instance, by not adhering to the prescribed timing of intervention, or by withdrawing from the study) will still be analyzed in the group to which they were assigned. We want to estimate the effects of using a PICO dressing at all in practice, not the effects in the subgroup of the participants who adhere to it. If patients receive a different type of dressing (intervention) accidentally from the one they were assigned, they will be excluded from the study in order to remove any bias that could arise from reasons why a provider chose to use that specific dressing instead of the assigned dressing.

In addition, a per-protocol analysis dataset will be analyzed (entire control group and PICO group who used the PICO NPWT dressing for a minimum of 5 days).

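### Section 9.3 keeps women who withdraw in their assigned group yet makes entry to the ITT analysis conditional on completing Visit 4, and Sections 9.4.2 and 9.4.3 give a third, different rule

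*Protocol*

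**What the plan says.** Protocol Section 9.3 sets out the primary analysis set in several statements:

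- The set is a modified ITT: women who had the operation and were given the intervention.
- "All subjects will be analyzed according to the intention-to-treat [ITT] principle".
- A woman "will be considered evaluable and will be included in the intention-to-treat analysis if the patient has completed all phases of the study", the last of these being Visit 4 at day 42±10.
- Women who depart from the protocol, for instance by "withdrawing from the study) will still be analyzed in the group to which they were assigned".
- "If patients receive a different type of dressing (intervention) accidentally from the one they were assigned, they will be excluded from the study". The reason given is bias arising from "reasons why a provider chose to use that specific dressing instead of the assigned dressing".

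The section says its choice is meant to avoid "misleading artifacts that can arise in intervention research such as non-random attrition of participants from the study or crossover". It names its target: "We want to estimate the effects of using a PICO dressing at all in practice, not the effects in the subgroup" of adherers. A per-protocol analysis is planned as secondary.

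Other sections bear on the same women. Section 9.2 calls a woman evaluable "if she has completed all phases of the study including the last visit of the last scheduled procedure" and sizes the trial on that group. Sections 9.4.2 and 9.4.3 handle non-adherence and loss to follow-up by reporting the data as missing, with the reason, and analysing all the data that are available. Section 7.2 has treated women who later withdraw replaced. Section 8.1 obtains SSOs from routine visits and from chart review, including unscheduled visits.

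**The concern.** Two analysts following this protocol could build different primary sets. One would keep a woman who withdrew in week 2, and the other would drop her because she never reached Visit 4. If she already had an SSO noted on post-operative day 1, at the day 7–14 visit or in the chart, the completer rule throws that event away.

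The completer rule selects on something that happens after randomisation, in an open-label trial whose endpoint is judged by clinicians. If the women who miss Visit 4 differ in risk between arms, the comparison among completers is distorted. If the set is settled only after the data are visible, the choice itself could affect the result.

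The wrong-dressing exclusion also selects after randomisation. It removes the crossover cases that the section says its approach is there to handle.

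**Working it through.** **1. The rules side by side.** Take a woman who was operated on, received her assigned dressing, had an SSO recorded at the day 7–14 visit and then withdrew.

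| Rule | Her place in the primary analysis |
|---|---|
| Modified ITT (9.3) | in |
| All subjects by ITT (9.3) | in |
| Withdrawals still analysed (9.3) | in |
| Visit 4 completion (9.3; *evaluable* in 9.2) | out |
| Report as missing, use available data (9.4.2, 9.4.3) | in, with her SSO |

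No other section resolves this.

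**2. The plan's own sample size.** Inputs from 9.2: 18% v 8%, alpha 5% (taken as two-sided), power 80%, attrition 10%. With pooled variance and p̄ = 0.13:

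n = [1.96·√(2·0.13·0.87) + 0.8416·√(0.18·0.82 + 0.08·0.92)]² / 0.10² = (0.9322 + 0.3958)² / 0.01 = 176.4, so 177 per group.

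The plan states 180, which gives power 80.8%, and 180/0.90 = 200. The odds ratio (0.08/0.92)/(0.18/0.82) = 0.396 also reproduces. The sample size arithmetic is sound.

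**3. Number of women affected.** 200 × 0.10 = 20 per arm, if withdrawn women are not replaced.

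**4. What the completer rule could do (illustration).** The documents give no risk for non-attenders, so these values are assumed. True SSO risk is 18% in both arms, 10% miss Visit 4, and r is the risk among those who miss it.

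Completer risk = (0.18 − 0.10·r)/0.90, which is 17.0%, 16.0% or 14.4% for r = 27%, 36% or 50%.

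The chance of a false finding in favour of PICO comes from exact binomial enumeration of the uncorrected two-sided 5% chi-square test, 180 v 180 (nominal 2.5%):

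| Excess risk among non-attenders | r = 27% | r = 36% | r = 50% |
|---|---|---|---|
| PICO arm only | 4.3% | 7.3% | 14.8% |
| Control arm only | 1.4% | 0.7% | 0.2% |
| Both arms equally | 2.5% | 2.5% | 2.5% |

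**5. Wrong-dressing exclusion (illustration).** No wrong-dressing rate is given. Assume a fraction w of one arm is removed and those women have 36% risk. The remaining risk is (0.18 − 0.36·w)/(1 − w): 17.6% for w = 2% (196 v 200) and 17.1% for w = 5% (190 v 200). The false-positive rate for PICO is 3.1% or 4.4% if they leave the PICO arm, and 2.0% or 1.4% if they leave control.

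**6. Why a single missing-outcome rule is needed.** Assume 18% v 8%, 20 non-attenders per arm at average risk, and half of their SSOs recorded before loss. Recorded SSOs are then 32.4 + 1.8 = 34.2 in control and 14.4 + 0.8 = 15.2 in PICO.

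- Counting the remaining non-attenders as event-free: 34.2/200 = 17.1% v 15.2/200 = 7.6%, a difference of 9.5 points.
- Keeping only non-attenders with a recorded SSO: 34.2/181.8 = 18.8% v 15.2/180.8 = 8.4%, a difference of 10.4 points.

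The planned difference is 10 points, so neither shortcut recovers it exactly.

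**The case against.** **The available-data rule already saves the recorded events.** Sections 9.4.2 and 9.4.3 say to use all available data, and 9.4.1 plans a mixed model on repeated measures that can use earlier visits. This stands in part: discarding a recorded SSO is one of two readings. A reader might infer that the protocol settles on losing these events, and it does not. But it does not settle on keeping them either, because 9.3 still governs who enters the analysis.

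**The text says *if*, not *only if*.** Read loosely, completing Visit 4 need not be the sole way in. But the sentence defines who is evaluable and included, and 9.2 powers the trial on exactly that group. On the loose reading it would do nothing.

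**The wrong-dressing exclusion belongs to the modified ITT.** This largely stands. The rule is stated and can be carried out, so it is not a logical impossibility. It conflicts with the section's ITT principle, with its concern about crossover and with its target. Its rationale also speaks of provider choice while the rule speaks of accident.

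**The statistical analysis plan can sort it out.** An analysis plan may supply detail, such as the imputation method. Here the protocol has already fixed rules that conflict, and any later plan must override one of them.

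**The false-positive figures are hypothetical.** They are. The upper value needs 50% risk in PICO non-attenders against 18% in control non-attenders, and nothing in the documents supports that asymmetry. Section 7.3 also plans telephone calls, a letter and rescheduling to limit loss.

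**Replacement changes the counts.** Section 7.3 treats unreachable women as withdrawn and 7.2 replaces treated women who withdraw. Reaching 200 completers per arm would then take about 200/0.90 = 222 randomised. The figure of 20 per arm therefore holds before replacement.

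**Conclusion.** The contradiction is established from the text alone: withdrawals are kept, entry is tied to Visit 4, and two further sections use all available data. It concerns the primary analysis set and should be resolved before analysis. The wrong-dressing exclusion is a secondary point: executable, but at odds with the section's stated purpose.

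The size is about 20 women per arm at 10% attrition without replacement. A reader might infer that the primary result will be biased towards PICO. The documents do not support that. The direction depends on who misses Visit 4 and in which arm. Bias is nil in these illustrations if the women removed carry average risk, or the same excess in both arms with no true effect; then only power is lost. The false-positive ranges (4.3% to 14.8%, or 1.4% to 0.2%, against 2.5%) rest on assumed risks and show what could be at stake, not what is expected. Nor does the point show any fault in the sample size, which reproduces.

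**What to change.** 1. In 9.3, define the primary set as all randomised women who had the cesarean and received a study dressing, analysed as assigned whichever dressing was worn. Randomisation takes place at the start of surgery (6.3), so report by arm, with reasons, any randomised woman who received neither dressing.
2. Delete Visit 4 completion as a condition of entry and keep *evaluable* for sample size only. Delete the wrong-dressing exclusion, report those cases as deviations, and keep the per-protocol analysis as secondary.
3. Count any SSO recorded at any visit or in the chart up to the end of the final window. Bring 9.3, 9.4.2 and 9.4.3 under one missing-outcome rule, so that a woman with no recorded SSO and incomplete follow-up is neither silently event-free nor dropped. Multiple imputation within arm is one option. Add a best/worst-case check.
4. State that treated women who are replaced under 7.2 stay in the primary analysis.

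The cost is protocol wording, one rule and one sensitivity check; no new visits or data are needed. The downside is dilution from keeping wrong-dressing women. If 2% of each arm wore the other dressing, the rates become 0.98·18 + 0.02·8 = 17.8% and 0.98·8 + 0.02·18 = 8.2%; at 5% they become 17.5% and 8.5%. Power (normal approximation, pooled variance), before any replacement:

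| Wrong dressing, each arm | 200 observed outcomes per arm | About 180 observed per arm |
|---|---|---|
| None | 84.7% | 80.8% |
| 2% | 81.7% | 77.5% |
| 5% | 76.5% | 72.0% |

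The 200 column requires every non-attender's outcome to be known, which imputation does not achieve, so the 180 column is the more cautious guide.

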## 6 STUDY INTERVENTION

### 6.1 STUDY INTERVENTION(S) ADMINISTRATION

#### 6.1.1 STUDY INTERVENTION DESCRIPTION

The PICO Single Use Negative Pressure Wound Therapy Device (Smith and Nephew Healthcare, Hull, United Kingdom) is a non-significant-risk, FDA Class II, medical device commercially available in the USA. The PICO unit is a single patient use, battery-powered, disposable unit that can provide continuous 80 - 125 mmHg negative pressure over a 5 to 7-day therapy period. It is an easy to use device that also provides audible and visual alerts for low battery, maximum canister volume, and leak conditions. Additional alerts include system error and device life-cycle expiration (7 days). It is contained in a water-resistant housing, which allows the subject to lightly shower with the device. Wound fluids are contained within the 45 mL canister.

The dressing is applied to the wound and extra strips are placed over the outside edge to help hold the dressing in place. When the pump is turned on, air is pulled out of the dressing and excess fluid from the wound will start to enter the dressing. The dressing helps to prevent bacteria from entering the wound. It may also improve blood flow to the wound which will help it to heal.

The standard-of-care is consistent with the national standard for dressing Cesarean section incisions and includes, but not limited to, coverage of the sutured incision with sterile gauze and non-penetrable barrier (e.g., Tegaderm™). The non-penetrable barrier may be left in place for a minimum of 1 day and no longer than 2 days ( $\pm$  4 hours) to promote epithelialization of the surgical incision edges. After the dressing is removed, the surgical site is left exposed to air to promote further healing. Other therapies include traditional gauze dressings with or without advanced therapies such as hydrocolloids, growth factors, and Negative Pressure Wound Therapies.

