#### 6.4 STUDY INTERVENTION COMPLIANCE

In order to complete the study intervention, the participant must have worn the PICO NPWT dressing for a minimum of 5 days after surgery. On the fifth postoperative day, the participant may remove the dressing at home. A phone call to each participant randomized to the PICO NPWT dressing will be made on the 5th or 6th postoperative day (after discharge to the hospital) to verify compliance with the use of the device. No documents are mandatory for the participants to complete and adherence to the protocol will be verified by patient report only.

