### 7 STUDY INTERVENTION DISCONTINUATION AND PARTICIPANT DISCONTINUATION/WITHDRAWAL

#### 7.1 DISCONTINUATION OF STUDY INTERVENTION

Discontinuation from PICO dressing compliance before a minimum of 5 days does not mean discontinuation from the study, and remaining study procedures should be completed as indicated by the study protocol. If a clinically significant finding is identified (including, but not limited to changes from baseline) after enrollment, the investigator or qualified designee will determine if any change in participant management is needed. Any new clinically relevant finding will be reported as an adverse event (AE).

The data to be collected at the time of study intervention discontinuation will include the following:

- Reason the PICO dressing was discontinued:
  - Patient discomfort,
  - Misunderstanding of use,

- Loss of supplies,
- etc.
- Incision assessment
- SSI or SSO

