## 8 STUDY ASSESSMENTS AND PROCEDURES

## 8.1 EFFICACY ASSESSMENTS

Screening procedures and evaluations may be performed on the day of enrollment but no more than 10 days prior to the day of enrollment. The screening process will be a discussion with the patient and review of medical history and height and weight to determine eligibility, and explanation of the study rational and study protocol, and demonstration of the two dressing options. Informed consent will then be obtained and patients will have the opportunity to ask questions.

The study intervention will be administered at the end of the scheduled cesarean delivery procedure. Standard dressings will be removed on postoperative day 1 as per current protocol and PICO NPWT dressings will be changed if necessary in the hospital and removed on postoperative day 5 by the patient at home.

**Procedures that will be completed during the study as part of regular standard of clinical care:** the post-operative visits on day 7 – 14 and 42 +/- 10 days are part of regular standard of clinical care and the outcomes and incision assessments after the participating patients leave the hospital will be performed by skilled residents and attending physicians at these visits. Charts will be reviewed to ascertain if SSO/SSIs were diagnosed or SII were necessary.

During these regularly scheduled visits, a **physical examination and incision assessment** will be performed including weight, abdominal exam, incision exam, and all regular postoperative visit exams including breast and pelvic (at the 42 +/- 10 day visit only) as part of the routine standard of care.

If follow-up visits or unscheduled visits are required for treatment of SSO/SSIs or SII, information regarding the type of SSO or SII required will be obtained from review of the medical chart.

**Surgical Site Occurrences include:** unanticipated local inflammatory response, prolonged drainage, fluid collection, dehiscence, surgical site infection (SSI). SSI is diagnosed using the following criteria: warmth to touch, pain with palpation, skin redness, irritation, or induration, large amount of drainage or purulent drainage, fluctuance suspicious for wound abscess, fever, and/or wound odor.

**Surgical Site Interventions include:** Antimicrobials for surgical site infection, surgical drainage of the incision, surgical incision packing, adjunctive negative pressure therapy, debridement, or re-operation.

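### The per-protocol set selects on adherence in the PICO arm only, so the secondary per-protocol comparison is open to bias, probably in favour of PICO

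*Protocol*

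**What the plan says.** Protocol section 9.3 makes a modified intention-to-treat analysis primary and says that an analysis by treatment actually received "will be carried out as a secondary analysis (per protocol [PP] analysis"). It states the aim of the primary approach as the effect of using PICO at all, "not the effects in the subgroup of the participants who adhere to it". The per-protocol dataset is then fixed as the "entire control group and PICO group who used the PICO NPWT dressing for a minimum of 5 days".

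No wear condition applies to controls, although the protocol gives their dressing a timing of its own. Section 8.1 says: "Standard dressings will be removed on postoperative day 1 as per current protocol". Section 6.1.1 says that the barrier "may be left in place for a minimum of 1 day and no longer than 2 days".

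Adherence follow-up after discharge is also one-sided. Section 6.4 says: "A phone call to each participant randomized to the PICO NPWT dressing will be made", on day 5 or 6, and adds that "adherence to the protocol will be verified by patient report only".

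Section 7.1 keeps women who stop PICO early in the study. At that moment it collects the "Reason the PICO dressing was discontinued", an incision assessment, and whether an infection or SSO is present.

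**The concern.** Randomisation protects a comparison of the arms as randomised. It does not protect a comparison in which one arm has been thinned by something that happens afterwards and may share causes with the outcome.

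That link is plausible from the protocol's own text. Section 9.4.2 counts as SSO components redness, tenderness, warmth or induration, drainage at three or more days from surgery, fluid that needs the skin opened, and skin separation. All of these can arise inside the 5-day wear period, and some could lead to the dressing coming off. Section 7.1 puts discomfort first among its reasons for stopping and asks for SSO status at that point, so it allows for early removal and an outcome event coinciding. When they coincide, the event leaves the PICO arm of the per-protocol set, while the same event on the same day in a control is counted.

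At stake is how the secondary result is read. A per-protocol estimate more favourable than the primary one could be taken as evidence of efficacy in women who wear the device as intended, when part or all of the gap is selection. The statistical analysis plan is not at hand, but this is not a detail left to it: the protocol states the rule, and following it exactly produces the one-sided set.

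**Working it through.** **The plan's own figure first.** Section 9.2 gives 18% SSO on standard dressing, 8% on PICO, alpha 0.05, 80% power, 180 evaluable women per group, and 200 recruited at 10% attrition. Sidedness is not stated; two-sided is assumed here, because it comes close to the stated number and one-sided does not (139).

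n = [1.960·√(2·0.13·0.87) + 0.842·√(0.18·0.82 + 0.08·0.92)]² / 0.10² = 176.4, so 177 per group. Power at 180 is 80.8%, and 180/0.90 = 200. The design figure stands and does not depend on the per-protocol set.

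**Inputs for the bias.**
- From section 9.2: overall SSO risk p = 0.18, applied to both arms because no true effect is assumed; 180 evaluable women per arm.
- Assumed, because the protocol gives neither: f, the share of PICO women with less than 5 days of wear (10% and 20%), and R, the SSO risk in those women relative to adherers (0.5, 1, 2 and 3).

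**Formulas.** The PICO arm's overall risk is a mixture: p = (1−f)·a + f·R·a, where a is the adherers' risk. Hence a = p / [(1−f) + f·R]. The bias is p − a, positive when it favours PICO. The per-protocol comparison has 180 controls and 180·(1−f) PICO women, that is 162 or 144. The chance of a significant result favouring PICO is Φ[(p − a − 1.96·SE0)/SE1], where SE0 is the pooled and SE1 the unpooled standard error (normal approximation). With no bias it is 2.5%.

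**One case in full, f = 0.20 and R = 3.**
- a = 0.18/(0.80 + 0.60) = 0.1286, so the bias is 5.1 points.
- Pooled risk = (180·0.18 + 144·0.1286)/324 = 0.1571.
- SE0 = √[0.1571·0.8429·(1/180 + 1/144)] = 0.0407.
- SE1 = √[0.18·0.82/180 + 0.1286·0.8714/144] = 0.0400.
- Φ[(0.0514 − 1.96·0.0407)/0.0400] = Φ(−0.71) = 23.9%.

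**Results with no true effect**

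| f | R | SSO risk in PICO adherers | Bias (points, + favours PICO) | Significant in favour of PICO |
|---|---|---|---|---|
| 10% | 0.5 | 18.9% | −0.9 | 1.5% |
| 10% | 1 | 18.0% | 0.0 | 2.5% |
| 10% | 2 | 16.4% | +1.6 | 5.9% |
| 10% | 3 | 15.0% | +3.0 | 11.1% |
| 20% | 0.5 | 20.0% | −2.0 | 0.8% |
| 20% | 1 | 18.0% | 0.0 | 2.5% |
| 20% | 2 | 15.0% | +3.0 | 10.5% |
| 20% | 3 | 12.9% | +5.1 | 23.9% |

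For scale, the design difference is 18% − 8% = 10 points.

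**The case against.** A reader might infer that the set favours PICO by construction. The protocol does not support that. The definition creates the selection; its direction and size depend on why women stop. Two of the three reasons that section 7.1 names, misunderstanding of use and lost supplies, have no evident link to the wound, and removal for a wound problem is not itself listed (the list is open-ended). Section 8.1 lets PICO dressings be changed in hospital, and section 6.2.2 says each pack holds two so that the wound can be inspected, so an early wound problem need not end wear. If removal is unrelated to SSO the bias is zero, and if early removers are at lower risk it runs against PICO. This stands. Bias towards PICO is the likelier direction, not a certain one.

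The impact is also limited by the text. The analysis is already called secondary, early removers stay under follow-up, and the primary analysis does not apply the 5-day rule. Nothing says how prominently the per-protocol result will be reported. This stands too, and it keeps the point below the level of a threat to the primary conclusion.

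Finally, the one-sidedness suggests an obvious repair, a matching wear rule for controls, and that repair would do little. The control dressing comes off within a day or two of surgery, so such a rule would probably exclude few women. The problem is selection on PICO wear. That adherence rests on patient report is a separate, measurement issue; it matters here because it limits how well any repair can be carried out.

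What survives is that the rule is explicit, leaves one arm open to outcome-related exclusion, and can be changed cheaply.

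**Conclusion.** The point holds as a weakness of the secondary per-protocol analysis. The set conditions on post-randomisation wear in the PICO arm only, so the comparison is not protected by randomisation and is open to bias, probably in favour of PICO.

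For early removers at two to three times the adherers' risk, the chance of a significant result favouring an ineffective device is 5.9% to 23.9%, against 2.5% nominal. These figures rest on assumed early-removal rates and relative risks, on 18% SSO in both arms, and on a normal approximation. They show what the rule permits and are not a forecast. More extreme assumptions give more: 20% early removal with a 40% SSO risk leaves adherers at (0.18 − 0.08)/0.80 = 12.5% and puts the chance at about 27%. But that requires 0.08/0.18 = 44% of the PICO arm's SSOs to fall in the fifth of women who stopped early, and it should not be used as the headline.

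The sample size and the error rate of the primary analysis are not affected by this rule.

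**What to change.** Amend the per-protocol definition in section 9.3 in one of two ways:
- Do not exclude PICO women whose early removal was prompted by a wound problem or an SSO. Section 7.1 already collects the reason, the incision assessment and SSO status at stopping, so no new data item is needed.
- Or replace the set by an adherence-adjusted estimate, such as a complier-average effect, that keeps all women in the primary analysis set.

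In either case, state that the result is supportive only, and report the number of PICO women excluded or classed as non-adherent, with their SSO rate, so that a reader can judge the direction of any selection.

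A control-arm adherence criterion is optional and would change little. It cannot be written until sections 6.1.1 and 8.1 on control dressing removal are reconciled.

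The cost is a changed definition and a small amount of analysis and reporting. Neither option is clean. The recorded reasons for removal are unblinded and partly patient-reported, so misclassification can remain under the first. A complier-average estimate assumes no effect in non-compliers, which is doubtful for a woman who had a few days of PICO. Both limits should be stated with the result.
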